#### 9.4 Outcomes

The goal of this study is to supply patients and families with the information about the risks and benefits of PFDD and PFD that *they feel* are most important in making informed clinical decisions. As such, the primary outcome of interest is reduction in harm to patients, measured as surgical complications and/or requirement for reoperation for complication management  $\leq 12$  (+/- 2 months) months after initial PFDD or PFD. Complications and reoperation are associated with additional pain as well as emotional and psychological stress, longer hospital stays, and lost time from school/work. Secondary outcomes focus on efficacy outcomes and will include: 1) comparison of pre-operative symptoms and neurological deficits at  $\leq 6$  weeks, 3-6 months, and 12 (+/- 2 months) months after surgery and syrinx size and spinal alignment (coronal and sagittal Cobb angles) at 12 (+/- 2 months) months after surgery; and 2) assessment of QOL (including psychosocial and physical dimensions) at baseline,  $\leq 6$  weeks, 3- 6 months, and 12 (+/- 2 months) months after surgery. This outcome will be evaluated using the CHIP and the HUI-3 QOL instruments.

Because this is a surgical trial, an Adjudication Committee, consisting of two pediatric neurosurgeons and one pediatric neuroradiologist and independent of the design and conduct of the trial, will adjudicate the primary outcome measure. The committee will review the primary endpoint based on a blinded review of clinical notes, data forms and imaging studies. Decisions by the adjudication committee will determine final outcomes. Consensus definitions of CSF-related complications following neurosurgery have been developed [34]. These definitions have been reviewed and approved by the neurosurgeons participating in the study, and will be used in this trial. Likewise, the extent of syrinx resolution following surgery will be determined by centralized review of blinded imaging studies. By contrast, treatment failure (i.e. need for revision PFDD or PFD) will be determined individually by the treating surgeon in consultation with the patient/family, since such decisions are inherently subjective and based both on the surgeon's level of concern and the patient's discomfort and relative acceptance to the inherent risks of surgery (either PFD or PFDD).

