#### Comparison methods

The primary outcome is a binomial outcome measured as a surgical complication and/or requirement for reoperation for complication management  $\leq 6$  months after initial PFDD or PFD. To account for within cluster correlation, possibly variable cluster size and the relatively small number of clusters in this cluster randomized trial, generalized estimating equations (GEE) with small-sample correction or random effect logistic regression will be used for the primary analysis of this cluster randomized trial [35, 36].

Secondary outcomes include Treatment Efficacy variables and Quality of Life variables. Continuous variables measured at 3 time points over the 12 (+/- 2 months) month follow-up will be analyzed using longitudinal analysis with linear mixed models including the random cluster effect. Binomial and ordinal data will be analyzed using GEE methods accounting for cluster. In the case where the patient returned outside the planned study follow-up window, a secondary analysis will include those visits up to 24 months.

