1.1 Primary Objective

Specific Aim 1: Determine if PFD is associated with fewer surgical complications and less harm to patients than PFDD.

Hypothesis: PFD will be associated with fewer surgical complications and less potential harm to patients than PFDD.

Anticipated Outcome: Cerebrospinal fluid (CSF)-related complications ≤ 6 months (e.g. CSF leak, pseudomeningocele, aseptic meningitis, infection, hydrocephalus), and the requirement for additional surgery for wound revision or CSF diversion will be lower after PFD compared with PFDD.

Corresponding Variable Names for 'Complications':

- **CSF leak:** Form 16634 (10), ChiariPOCSFLeak
- **Pseudomeningocele:** Form 16402 (4), ChiariPOPseudomen
- Aseptic meningitis: Form 16420 (5), ChiariPOchemicalMeningitis
- True meningitis: Form 16416 (5), ChiariPOTrueMeningitis
- Infection: Form 16416 (5), ChiariPOWRInfection
- Hydrocephalus: Form 16427 (6), Hydrocephalus
- Cervical Instability: Form 16431 (6), CervicalInstability

Corresponding Variable Names for 'Additional Surgery for Wound Revision or CSF Diversion'

- Required External drainage of CSF: Form 16404 (4), ChiariPOExtDrainageCSF
- Simple Over-Sewing of Wound for CSF Leak: Form 16413 (5), SimpleOSWoundCSF
- Surgical revision of wound in operating room: Form 16414 (5), ChiariPOSurgRevision
- Chemical Meningitis: Form 16420 (5), ChiariPOchemicalMeningitis
- CSF Leak: Form 16415 (5), ChiariPOWRCSFLeak
- Infection: Form 16416 (5), ChiariPOWRInfection
- **Pseudomeningocele:** Form 16419 (5), ChiariPOWRPseudomen

Outcome –Count, Number of patients with a complication

Timeframe - ≤ 6 months

Time Period	Complication			
Intra-Op				
	Vascular Injury			
	Hemorrhage Requiring Evacuation			
	Neurological Injury			
	Death			
	Other Complications			
< 6 Months				
	Pseudomeningocele			
	CSF Leak			
	External Drainage Required			
	Simple Over-Sewing of Wound for CSF Leak			
	Surgical Revision of Wound in OR			
	Chemical Meningitis			
	True Meningitis			
	Hydrocephalus			
	Cervical Instability			
	Other Complications, Procedure Specific			
	Other Complications, Not Procedure			
	Specific			
> 6 Months				
	Cervical Instability			
	Infection			
	Hydrocephalus			
	Other Complications, Procedure Specific			

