For the purpose of sample size estimation, data from in the Park-Reeves Syringomyelia Research Consortium (PRSRC) were analyzed (ambispective enrollment, n=589 subjects with complete data); specifically, surgical complications ≤ 12 months were used to calculate the sample size. In this dataset, surgical complications were noted in 17.8% of PFDD cases and 2.7% of PFD cases. This is consistent with reported values from a recent meta-analysis, where the rates for CSF-related complications for PFDD and PFD were 18.5% and 1.8%, respectively [27], as well data reported in case series [17, 25] and a systematic review [42]. We expect to observe a similar difference in PFDD versus PFD cases in the proposed study. Because of the clustered randomized nature of the trial, the intraclass correlation coefficient (ICC) should be taken into account. The ICC is defined as the proportion of the between cluster (PRSRC center) variation to the total variation. Since the cluster sizes are small (6 per PRSRC center), and we have a large number of centers available for enrollment (47 total), the effect of ICC on sample size will be small. Thus, using the PRSRC values of 17.8% for PFDD and 2.7% for PFD, and assuming equal number of subjects per group and twosided type I error rate of 0.05, to reach 90% power, 36 centers averaging 6 subjects per center will be required for the trial assuming the ICC is 0.05. To account for 2% dropout rate, we originally planned to recruit 40 centers with a cluster size averaging 6 subjects with overall sample size of enrolled patients of 240 patients, approximately 120 patients per procedure over the two years of enrollment.

Aim 1: Sample Size Recalculation (November 29, 2017)

The original sample size calculation was performed based on surgical complication rates (≤ 12 months) from Park-Reeves Syringomyelia Research Consortium (PRSRC) estimates (17.8% in PFDD and 2.7% in PFD cases). We originally did not have an estimate for the ICC. Based on the literature, we assumed ICC of 0.05 in our calculations [43]. The overall sample size of enrolled patients would be 240 patients, approximately 120 patients per procedure over the two years of enrollment.

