7.4 Outcomes

The goal of this study is to supply patients and families with the information about the risks and benefits of PFDD and PFD that *they feel* are most important in making informed clinical decisions. As such, the primary outcome of interest is reduction in harm to patients, measured as surgical complications and/or requirement for reoperation for complication management ≤ 12 (+/- 2 months) months after initial PFDD or PFD. Complications and reoperation are associated with additional pain as well as emotional and psychological stress, longer hospital stays, and lost time from school/work. Secondary outcomes focus on efficacy outcomes and will include: 1) comparison of pre-operative symptoms and neurological deficits at ≤ 6 weeks, 3-6 months, and 12 (+/- 2 months) months after surgery and syrinx size and spinal alignment (coronal and sagittal Cobb angles) at 12 (+/- 2 months) months after surgery. This outcome will be evaluated using the CHIP and the HUI-3 QOL instruments where analyses based on CHIP will be used as the primary results for aim 3 in case CHIP and HUI-3 results do not agree.

Because this is a surgical trial, an Adjudication Committee, consisting of two pediatric neurosurgeons and one pediatric neuroradiologist independent of the design and conduct of the trial, will adjudicate the primary outcome measure. The committee will review the primary endpoint based on a blinded review of clinical notes, data forms and imaging studies. Decisions by the adjudication committee will determine final outcomes. Consensus definitions of CSF-related complications following neurosurgery have been developed [34]. These definitions have been reviewed and approved by the neurosurgeons participating in the study and will be used in this trial. Likewise, the extent of syrinx resolution following surgery will be determined by centralized review of blinded imaging studies. By contrast, treatment failure (i.e. need for revision PFDD or PFD) will be determined individually by the treating surgeon in consultation with the patient/family, since such decisions are inherently subjective and based both on the surgeon's level of concern and the patient's discomfort and relative acceptance to the inherent risks of surgery (either PFD or PFDD).

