The primary outcome is a binomial outcome measured as a surgical complication and/or requirement for reoperation for complication management ≤ 12 (+/- 2 months) months after initial PFDD or PFD. To account for within cluster correlation, possibly variable cluster size and the relatively small number of clusters in this cluster randomized trial, generalized estimating equations (GEE) with small-sample correction or random effect logistic regression will be used for the primary analysis of this cluster randomized trial [35, 36].

Specifically, a GEE model with a logit link function and adjustment for baseline covariates can be expressed as follows:

$logit(\pi_{ij}) = \mu + \delta T_i + x_{ij}\beta$

where $T_i = I$ if group *i* is assigned PFD and 0 otherwise. Accordingly, δ is the intervention effect. Let x_{ij} is the p-dimensional vector of group-level of individual level covariates from individual *j* (*j* = 1, ..., n_i) nested in center *i* (*i* = 1, ..., # of active centers here); and β is the vector of covariate effects. Also let the outcomes (CSF-related complication ≤ 6 months, yes/no) are independently distributed as $y_{ij} \sim \text{Bernoulli}(\pi_{ij})$. Further let, μ be the log-odds of positive outcome ($y_{ij} = 1$) for PFDD subjects with reference values for covariates ($x_{ij} = 0$) and average random effect ($\gamma_i = 0$). The exchangeable correlation structure will be used for the within-group homogeneity for the correlation structure of the outcomes. Note that, this correlation parameter corresponds to the intraclass correlation coefficient (ICC).

Specific Aim 2:

Hypothesis: Clinical improvement and syrinx regression provided by PFD will be non-inferior compared to those provided by PFDD.

Anticipated Outcome: Clinical symptoms, neurological function, and syrinx regression ≤ 12 months (± 2 months) provided by PFD will be non-inferior compared to those provided by PFDD. The non-inferiority margin is defined as the difference between the outcome rates by treatment. For the clinical improvement outcome, a non-inferiority margin of 0.17 units will be used. A non-inferiority margin of 0.135 units will be used for the syrinx regression outcome.

Clinical symptoms, neurological function, and syrinx regression are defined as rates of change from baseline to 12 months. The 1-sided confidence interval for the difference in rates between the PFD and PFDD groups will be calculated and compared to the corresponding non-inferiority margins.

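### The primary endpoint has two windows (≤6 months and ≤12 ±2 months), and the SAP's primary GEE model uses a ≤6-month, CSF-related outcome

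*SAP*

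**What the plan says.** **12 (±2) months.** SAP 7.4 describes harm as "measured as surgical complications and/or requirement for reoperation for complication management ≤ 12 (+/- 2 months) months after initial PFDD or PFD". Protocol 9.4 uses the same phrase ("measured as surgical complications and/or requirement for reoperation for complication management") and ends it with 12 (±2) months. The sentence that opens the Aim 1 methods in SAP 7.5 counts a surgical complication and/or "requirement for reoperation for complication management ≤ 12 (+/- 2 months) months after initial PFDD or PFD". The primary-outcome lists in Protocol 10.3.3 and SAP 7.5.1 carry the same window.

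**6 months.** SAP 1.1, under the primary objective, gives "Timeframe - ≤ 6 months", although the table beneath it also has rows for events after 6 months. Protocol 9.5 (Comparison methods) begins "The primary outcome is a binomial outcome measured as a surgical complication and/or requirement for reoperation for complication management" and ends that sentence with ≤6 months. The SAP 7.5 model then states "Also let the outcomes (CSF-related complication ≤ 6 months, yes/no) are independently distributed as".

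**Sizing.** SAP 7.2.1 says of the consortium data: "specifically, surgical complications ≤ 12 months were used to calculate the sample size". The rates are 17.8% for PFDD and 2.7% for PFD. For comparison it cites a meta-analysis "where the rates for CSF-related complications for PFDD and PFD were 18.5% and 1.8%, respectively", with no window stated.

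**The concern.** A programmer who codes the outcome from the model paragraph will not produce the endpoint defined a few lines above it. The window is halved. On its face the CSF-related label also removes components that SAP 7.5.1 counts as harm: vascular injury, hemorrhage needing evacuation, neurological injury and death. How much the label removes is itself unsettled, because SAP 1.1 puts cervical instability and intra-operative rows under its ≤6-month heading.

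This is the trial's main comparison, and no section calls one version primary and the other a sensitivity analysis. The SAP is dated July 2021. Enrollment was proposed to end on 31 December 2018; if that date held, 14-month follow-up would have ended around the end of February 2020. Two usable definitions at that stage leave a choice that should not be made with results by arm in view.

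**Working it through.** **1. The definitions side by side**

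| Place | Event | Window |
|---|---|---|
| Protocol 9.4 | complication and/or reoperation for complication management | ≤12 (±2) months |
| Protocol 10.3.3 | any listed complication or procedure | ≤12 (±2) months |
| Protocol 9.5, Comparison methods | complication and/or reoperation | ≤6 months |
| SAP 1.1 | number of patients with a complication | ≤6 months (table also has >6-month rows) |
| SAP 7.4 | complication and/or reoperation | ≤12 (±2) months |
| SAP 7.5, Aim 1, opening sentence | complication and/or reoperation | ≤12 (±2) months |
| SAP 7.5, Aim 1, GEE model | CSF-related complication | ≤6 months |
| SAP 7.5.1 | any listed complication or procedure | ≤12 (±2) months |

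**2. Which window was probably meant.** The opening sentence in SAP 7.5 repeats the Protocol 9.5 sentence with 6 months changed to 12 (±2). Protocol 9.1 and SAP 7.1 place the central hypothesis at 12 (±2) months. The model paragraph also mentions a random effect, γ_i, that is not in its equation, which is a sign of carried-over text. All this points to an update that missed some places. It is inference, since no section settles it.

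**3. The plan's own figure.** Inputs from SAP 7.2.1: p1 = 0.178, p2 = 0.027, two-sided α = 0.05, 84% power, equal arms. The mean rate is 0.1025.

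n per arm = [1.96·√(2 × 0.1025 × 0.8975) + 0.994·√(0.178 × 0.822 + 0.027 × 0.973)]² / 0.151² = [1.96 × 0.4289 + 0.994 × 0.4154]² / 0.0228 = 68.9, rounded up to 69, or 138 in total. The unpooled-variance version gives 134. The stated 136 lies between them. With the design effect, 136 × 1.05 = 142.8, or 143. The arithmetic is sound, but it belongs to surgical complications within 12 months.

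The sizing rates count complications only. In Protocol 7.2.1, Table 3, the PFDD complication rows sum to 92 (1+28+20+2+24+15+2), and 92/516 = 17.8%. Procedures are totalled separately: 52/516 = 10.1%.

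**4. What the 6-month event could do to power.** The documents do not split events at 6 months, so the share falling within 6 months is an assumption, taken as equal in both arms. With 72 per arm and a design effect of 1.06, the effective size is 72/1.06 = 67.9, about the 68 per arm that the plan uses.

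Power = Φ{[(p1 − p2) − 1.96·√(2p̄(1 − p̄)/n)] / √[(p1(1 − p1) + p2(1 − p2))/n]}

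At 17.8% versus 2.7% and n = 68: (0.151 − 1.96 × 0.0520)/0.0504 = 0.974, so power is 83.5%.

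| Assumed share within 6 months | Consortium rates (17.8% v 2.7%) | External CSF-related rates (18.5% v 1.8%) |
|---|---|---|
| 100% | 83.5% | 90.6% |
| 90% | 78.8% | 86.9% |
| 80% | 73.3% | 82.1% |
| 70% | 66.9% | 76.2% |

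The range runs from a gain to a substantial loss, and nothing in the documents locates the trial within it.

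**5. Components also differ**

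| Item | Included | Not included |
|---|---|---|
| Cerebellar ptosis / cerebellopexy | Protocol 10.3.3; SAP 5.2 harms ≤6 months; cerebellopexy among SAP 5.2 interventions at 6-12 months | SAP 7.5.1; SAP 5.2 complications at 6-12 months (ptosis) |
| True or bacterial meningitis as a named complication | Protocol 7.1 and the 7.2 harm lists; SAP 1.1 and 5.2 | Protocol 10.3.3; SAP 7.5.1 |
| Cervical instability as a named complication | Protocol 10.3.3; SAP 7.5.1 | Protocol 7.1, list to 12 months |
| Leak, pseudomeningocele, meningitis named after 6 months | Protocol 7.2 lists | Protocol 7 list after 6 months; SAP 1.1 table |

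**The case against.** The best defence is that the intended endpoint is clear enough. Both Outcomes sections, both Metrics sections and the sentence that introduces the model say 12 (±2) months, and the equation is offered only as one way of expressing the model. That defence is largely right about intent. It also disposes of the reading that the model line is the plan's only definition of the binary outcome: SAP 7.5.1 and the opening sentence in SAP 7.5 define it too. What stands is that the paragraph describing the primary model still names another event, and that Protocol 9.5 calls a ≤6-month outcome primary in so many words.

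A reader might infer that the trial is underpowered for the modelled event. The documents do not support that. Every loss in the table depends on an assumed share, and the external CSF-related rates give higher power than the sizing rates when all events fall within 6 months.

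A reader might also infer that the Protocol 10.3.3 component list is right and the later SAP 7.5.1 list is in error. Nothing shows whether ptosis was dropped by mistake or by decision.

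Late events are not wholly uncovered. Protocol 7.2 captures complications for one year, and Protocol 7 records other surgery-related complications after 6 months and lists late revision for pseudomeningocele and lumbar puncture for true meningitis.

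**Conclusion.** The conflict is real and lies within each document as well as between them. Followed as written, the SAP's primary model analyses a different event from its primary endpoint. That alone requires correction before analysis, because it decides what the main result is a result about.

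The stated 84% power is reproduced for ≤12-month surgical complications and is not shown for a ≤6-month, CSF-related outcome. The size of any loss is unknown and may be nil, so power is not the reason to act. The documents do not show that anyone chose between the windows after seeing results; they only leave that choice open. Taking 12 (±2) months as the intended window is an inference from the weight of the text. The component and recording differences are secondary consistency points.

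**What to change.** In Protocol 9.5, SAP 1.1 and the SAP 7.5 model, replace the ≤6-month outcome with the 12 (±2)-month composite of Protocol 9.4 and SAP 7.4 and 7.5.1. State one event cut-off within that window, since 10 to 14 months is a visit window and does not say whether an event at month 13 counts. Then define y_ij as:

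- **1** if an adjudicated listed complication or complication-management procedure occurs between surgery and the cut-off;
- **0** if follow-up reaches the end of the window as defined with no event;
- **missing** if follow-up ends earlier with no event, handled by the existing missing-data plan (Protocol 9.5, SAP 7.5).

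The third category matters: coding early losses as event-free would empty the planned comparison of exclusion, last observation carried forward and Buck's method.

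Label any CSF-related ≤6-month analysis secondary. Make and date the choice without sight of outcomes by arm.

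As secondary edits, use one component list throughout and say whether ptosis/cerebellopexy, true or bacterial meningitis and cervical instability count. Reconcile the lists of events after 6 months. Check and report whether late leak, pseudomeningocele and meningitis were recorded, because rewording cannot recover data that were not collected.

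The cost is wording in both documents and one data check. N does not change.

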complications are remarkably consistent with those reported in the meta-analysis by Durham and Fjeld-Olenec in 2008 (Table 2)[27], with complications noted in 17.8% following PFDD versus 2.7% after PFD. In addition, a corrective neurosurgical procedure for complication management was needed more often after PFDD compared to PFD (10.1% versus 2.7%). However, repeat decompression surgery for persistent disease was required in only 5.0% of PFDD cases versus 12.3% after PFD.

In planning a clinical trial for CM+SM, it is important to select appropriate inclusion criteria for study patients in order to: 1) enhance homogeneity in disease severity among study participants; 2) permit appropriate comparisons across participants and groups; and 3) ensure clinical equipoise among treating physicians. With this goal in mind, our group recently created the Chiari Severity Index, or CSI, a pre-operative instrument that stratifies children with CM+/-SM based on their probability of postoperative improvement[12]. The CSI was developed in conjunction with patient and families and uses their input as a critical arbiter of outcome. Two advanced methodologies, sequential sequestration and conjunctive consolidation, were used to identify key clinical and radiographic predictors of clinical outcome and then to integrate them into one useful CSI (Fig. 3).

We also recently completed a systematic review of outcome methods used in studies of CM+SM and noted that studies of CM+SM were significantly impeded by inconsistent and limited methods evaluating clinical of outcomes[28]. The majority of papers used a clinician's "gestalt" impression of symptomatic improvement (Fig. 4). Only 3 papers used scales validated in patients with CM+/-SM, and only 7 articles incorporated patient-response instruments. Our review emphasized the need for CM+SM-specific patient-based instruments to improve research in this field [28].

**Figure 3**. The Chiari Severity Index, or CSI, was developed using sequential sequestration of pre-operative clinical and radiographic parameters, followed by conjunctive consolidation of independent clinical and radiographic indices via [12]. Syrinx size was the only radiographic measure associated with clinical outcome, with a critical threshold of 6 mm diameter.

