The non-inferiority margins for this trial were determined in conjunction with a panel of experts on CM+SM and related treatment (the Park-Reeves investigators), our non-physician stakeholder partners, and our patient partners, [name], [name], [name], [name], [name], [name], and [name]. Using a clinical, Delphi-type approach [46] for the complex measure of clinical improvement, the research team agreed upon a non-inferiority margin of no more than 20% lower response for PFD from the PFDD group. The clinical improvement rate (the improvement from baseline to 12 months) for the PFDD group was provided as 78.6% in the Durham study [27]. Thus, with the sample size of 72 subjects per group (after an assumed 2% dropout), we can conclude the non-inferiority of the PFD to PFDD with a margin of 0.17 units (α =0.05, 80% power). This corresponds to clinical improvement rate of 61.6% in the PFD group. It was shown in the Durham study that the clinical improvement following PFD was 64.6%.

Determine if PFD provides non-inferior clinical improvement compared to PFDD (Non-inferiority Design)							
Outcome	PFDD	PFD	Data Source	Non-inferiority Margin	α-level	Subjects per group	Power
Clinical Improvement	44/56 (78.6%)	51/79 (64.6%)	Durham [27]	0.17	0.05	72	80%

For these calculations, the drop-out rate is assumed to be 2%, and the one-sided type I error rate is 0.05.

After determination with the Delphi method, the non-inferiority margin was subsequently confirmed as appropriate using Rothman's 95-95 approach [47, 48] and the FDA guidelines for selecting the non-inferiority margin for non-inferiority clinical trials [49]. Using these methods, the non-inferiority margin was estimated using the effect of the standard treatment (PFDD) from Durham's meta-analysis [27], with the lower 1-sided 95% confidence interval for the random-effects meta-analysis calculated to be used as a non-inferiority margin. When the data from the PFDD group from the Durham study was used for the clinical improvement outcome, the 95% lower 1-sided confidence interval from the random effects model was calculated as 0.611. In our proposal, we defined the non-inferiority margin as the difference between the clinical improvement rates in the PFDD and PFD groups ($\pi_{PFDD} - \pi_{PFD}$). For the clinical improvement outcome, this corresponds to the non-inferiority margin of 0.786 – 0.611 = 0.175 units. Therefore, our

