recommended non-inferiority margin of 0.175 units for the clinical improvement outcome is consistent with the FDA-recommended largest acceptable non-inferiority margin of 0.175 units.

In contrast to clinical improvement, syrinx regression is an objectively measurable and easily quantifiable outcome. It is measured by comparing syrinx size on MRI scans obtained before and after surgery. When the effective sample size is 68 subjects per group, and assuming 89.1% syrinx regression rate in the PFDD group [27], the non-inferiority margin is 0.135 units to reach 81% power. A non-inferiority margin of 0.135 units represents no more than 13.5% reduction from the PFDD group in terms of syrinx regression. Note that a one-sided type I error rate of 0.05 was assumed, and the 'Two group test of equivalence in proportions' option in nQuery Advisor was used for the sample size calculations.

Determine if PFD provides non-inferior syrinx regression compared to PFDD (Non-inferiority Design)							
Outcome	PFDD	PFD	Data Source	Non-inferiority Margin	α-level	Subjects per group	Power
Syrinx Regression	261/293 (89.1%)	31/38 (81.2%)	Durham [27] and PRSRC	0.135	0.05	72	81%

For these calculations, the drop-out rate is assumed to be 2%, intra-class correlation coefficient is 0.05, and the onesided type I error rate is 0.05.

Aim 3: Power Calculations

Based on preliminary data using the Chiari Health Index in Pediatrics (CHIP)[50], we observed a 0.12±0.16 unit improvement in Quality of Life (QOL) scores following PFDD. Our sample size of 72/group (effective sample size of 68/group) will provide 82% power to detect a 0.20±0.16 unit improvement in CHIP QOL scores following PFD (α =0.05). Both from an analytical standpoint and from the view of PRSRC investigators and our patient partners, this value represents both a significant and meaningful increase in QOL

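### The Aim 2 non-inferiority interval names no baseline covariate, although the protocol identifies syrinx size and the Chiari Severity Index as predictors of clinical outcome and recruitment is with known arm

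*SAP*

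**What the plan says.** **The decision rule.** SAP 7.5, Specific Aim 2: "The 1-sided confidence interval for the difference in rates between the PFD and PFDD groups will be calculated and compared to the corresponding non-inferiority margins". The margins are fixed there too: "For the clinical improvement outcome, a non-inferiority margin of 0.17 units will be used" and "A non-inferiority margin of 0.135 units will be used for the syrinx regression outcome". No covariate is named. In the same section the Aim 1 GEE model includes a vector of covariates, although its members are not listed.

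**The predictors.** Protocol 7.2.1 describes the CSI as "a pre-operative instrument that stratifies children with CM+/-SM based on their probability of postoperative improvement". The caption of Figure 3 in that section adds: "Syrinx size was the only radiographic measure associated with clinical outcome, with a critical threshold of 6 mm diameter". The CSI does not appear in the SAP.

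**What is collected.** Protocol 6.1 and 6.2.2 put presenting symptoms and brain, cervical and thoracic MRI at baseline for every participant.

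**How children are recruited.** Centres learn their arm before enrolling anyone (Protocol 5.1). Families know it at consent (Protocol 6.2.2). A child whose surgeon strongly favours one procedure is left out (Protocol 4.3).

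**Where syrinx diameter is used.** SAP 7.5 uses it to form subgroups with interaction tests, as a predictor in Buck's imputation, and as a covariate in secondary and exploratory models. None of these is said to feed the non-inferiority interval.

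**The concern.** The decisive interval for a non-inferiority claim should use the strong baseline predictors that the trial already measures. Here there are two reasons.

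- **Precision.** Adjusting for a prognostic baseline variable narrows the interval.
- **Case mix.** When the arm is known before consent and surgeons may withhold children, the severity of enrolled cases can differ systematically between arms. Protocol 2.2 itself says that symptoms may resolve less well after PFD, so a PFD centre has a plausible reason to hold back harder cases. If that happened, an unadjusted interval could support non-inferiority partly because of who was enrolled. Selection in the other direction would cost power.

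The plan foresees imbalance in prognostic factors, but its remedy is to weight cluster summaries by their variance. That changes how much each centre counts. It does not make the children in the two arms comparable. The exploratory response model cannot stand in either, because it includes treatment complications and improved syrinx size, which arise after surgery.

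**Working it through.** **1. Reproduce the plan's power.** Inputs from SAP 7.2.1: for clinical improvement, a PFDD rate of 0.786, 72 per group and margin 0.17; for syrinx regression, a PFDD rate of 0.891, an effective 68 per group and margin 0.135. On the error rate: "Note that a one-sided type I error rate of 0.05 was assumed".

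With equal true rates, SE = √[2p(1−p)/n] and power = Φ(margin/SE − 1.645).

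- Clinical improvement: SE = √(2 × 0.786 × 0.214/72) = 0.0684; power = Φ(2.487 − 1.645) = 80.0%. The plan states 80%.
- Syrinx regression: SE = √(2 × 0.891 × 0.109/68) = 0.0534; power = Φ(2.526 − 1.645) = 81.1%. The plan states: "the non-inferiority margin is 0.135 units to reach 81% power".

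Both figures reproduce, and both are unadjusted. The clinical figure has no design effect. With clusters of 6 it would be 78.3% at an ICC of 0.01 (72/1.05 = 68.6 effective) and 71.9% at an ICC of 0.05 (72/1.25 = 57.6 effective).

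**2. Precision from adjustment, clinical improvement.** The documents give no improvement rates by syrinx size or CSI. Assume a two-level predictor present in half the children, with improvement differing by g between levels. Then R² = 0.25g²/(0.786 × 0.214), and SE is multiplied by √(1 − R²).

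| Assumed gap g | R² | Power | n per group for 80% |
|---|---|---|---|
| none | 0 | 80.0% | 72 |
| 0.10 | 0.015 | 80.5% | 71 |
| 0.20 | 0.059 | 82.1% | 68 |
| 0.30 | 0.134 | 84.8% | 63 |

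These figures treat the outcome as one 0/1 response per child and carry no design effect.

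**3. Shift from selective enrolment, clinical improvement.** Shift = imbalance × gap. Neither quantity is in the documents. Assume the better-prognosis share differs by 15 points between arms.

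- g = 0.20: 0.15 × 0.20 = 0.03, which is 0.03/0.17 = 18% of the margin.
- g = 0.30: 0.15 × 0.30 = 0.045, which is 0.045/0.17 = 26% of the margin.

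At a true difference equal to the margin (rates 0.786 and 0.616), SE = √[(0.786 × 0.214 + 0.616 × 0.384)/72] = 0.0750. If the shift favours PFD, the chance of declaring non-inferiority is Φ(shift/SE − 1.645): 10.7% for 0.03 and 14.8% for 0.045, against a nominal 5%. If it runs against PFD, power at equal rates is Φ((0.17 − shift)/0.0684 − 1.645): about 66% and 57%.

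For scale, the meta-analysis rates in SAP 7.2.1 differ by 78.6 − 64.6 = 14.0 points, which is 3 points inside the margin.

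**4. How far the assumptions carry the answer.** Imbalances of 10 to 30 points with gaps of 0.10 to 0.40 give shifts of 0.01 to 0.12, or 6% to 71% of the margin. The documents do not narrow that range.

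**The case against.** The other side has several good points.

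- **A reader might infer that the plan prescribes a crude difference.** SAP 7.5 does not use that word or say how the interval is estimated. It elsewhere assigns binomial secondary outcomes to mixed models that account for centre. But those models name no baseline predictor either, so the omission stands.
- **A reader might infer that the plan ignores severity.** It does not. Entry is limited to a 3-9 mm syrinx, which also limits how much diameter can explain. Syrinx subgroups are planned for every aim, and screening logs are reviewed for biased enrolment. None of this enters the verdict. The Appendix III log instructions ask for a number, a reason and initials, not severity.
- **A reader might infer that PFD centres enrol milder cases.** The documents show only that recruitment allows it. They show neither an imbalance nor its direction.
- **Chance imbalance is not a defect.** A valid interval already covers it. Only systematic selection biases the verdict, and adjustment removes only the part that is measured. Known-arm recruitment remains the underlying problem.
- **The precision gain is modest**, and close to nil if the predictors are weak.
- **The CSI may not be derivable.** The documents do not list its components, so their presence on the baseline forms is unverified. It combines clinical and radiographic indices, so entering the full grade beside diameter would probably count syrinx size twice.
- **The link is to clinical outcome.** No statement in the documents says that baseline diameter predicts syrinx regression.

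All of these limit the size and form of the point. None supplies the missing adjustment.

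**Conclusion.** The point holds as a worthwhile improvement to a secondary aim. The Aim 2 interval names no baseline covariate, although the protocol identifies predictors of clinical outcome, the trial collects the relevant MRI and symptoms, and recruitment is open to selection. The plan's remedy for imbalance does not correct case mix.

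Under the assumptions shown, adjustment is worth about 0.5 to 5 points of power for clinical improvement, and a 15-point selective imbalance would move the difference by 3 to 4.5 points of the 17-point margin. Protection against measured case-mix differences is the stronger reason to act.

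The documents do not support a claim that the Aim 2 result will be biased, that PFD will be favoured, or that power is seriously impaired. For syrinx regression the case rests on general good practice rather than on a predictor the documents establish.

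**What to change.** In SAP 7.5, Specific Aim 2, pre-specify the following.

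- **Clinical improvement.** The main comparison is a covariate-standardised PFD−PFDD difference, adjusted for continuous baseline syrinx diameter and, if they can be derived from the baseline forms, the clinical components of the CSI. Do not enter the full CSI grade together with diameter.
- **Covariates.** Exclude every post-operative variable.
- **Variance.** Use a centre-robust variance with small-sample correction.
- **Model.** Match it to the outcome. The primary binary scoring in SAP 1.2 averages each child's scores over visits and then over symptoms, which gives a fraction. If that is kept, use a fractional-response or linear model. Use a logistic model only if the outcome is a single 0/1 response per child.
- **Decision.** Compare the one-sided 95% limit with 0.17.
- **Syrinx regression.** Adjust for baseline diameter as a reasonable choice, state that the documents do not establish it as a predictor, and compare with 0.135.
- **Sensitivity.** Report the unadjusted difference alongside.

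The cost is SAP wording, a check of which CSI components are on the forms, slightly more analysis and some model dependence with few centres. No new visit is needed, and the margins stay as they are.
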